#### 14. STATISTICAL ANALYSIS AND REPORTING OF DATA

### 14.1. Statistical Considerations

The primary objectives of the Phase 1a portion of this trial are to assess the safety, tolerability, DLTs, and, if feasible, the MTD of AVID100 when administered by 2-hour\* IV infusion to patients with a histologically-documented, measurable or non-measurable, locally advanced or metastatic solid tumor malignancy of epithelial origin that is refractory to standard therapy or for which no standard therapy is available. These effects will be assessed by treating patient cohorts with sequentially escalating doses of AVID100. Other studies to be conducted during this trial include characterization of the pharmacokinetic profile of AVID100, and description of the preliminary antineoplastic activity of AVID100 in these same patient cohorts.

In addition, once the MTD is identified, the Phase 2a portion of the trial will enroll patients to 3 expansion cohorts of patients (approximately 60 patients total) with advanced (unresectable or metastatic) malignancies of epithelial origin (tumor types mTNBC, SCCHN, and Sq-NSCLC), and confirmed as expressing the EGFR and with measurable disease, will be entered to further evaluate tolerability and assess the preliminary antineoplastic activity of AVID100 in this patient population.

Data on safety and preliminary activity collected from additional patients added to the Phase 2a expansion cohorts will be summarized with patients treated at that same dose level in the Phase 1a portion of the trial. No tests of statistical inference will be performed.

\*Protocol v5.0: Extended from 1 hour to 1.5 hours due to Grade 3 IRR observed in Cohort 3 (80 mg/m²); effective 20Jul2017 and documented in a study Note to File dated 21Jul2017 (see **Section 2.3.2.1**; AVID100-01: Clinical Experience)

\*Protocol v6.0: Extended from 1.5 hours to 2 hours due to Grade 2 IRRs observed in Cohort 4(120 mg/m2); effective 21Dec2017 and documented in a study Note to File dated 28Dec2017 (see **Section 2.3.2.1**; AVID100-01: Clinical Experience)

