# 14.2. Sample Size Considerations

Sample size for the Phase 1a dose escalation portion of the study will be determined by safety observations, occurrence of DLTs, and the number of cohorts required to evaluate safety and choose an RP2D. It is assumed that approximately 4 cohorts will be required to determine the MTD, thereby enrolling approximately 14-30 patients during the dose escalation phase of the study. However, the protocol allows for enrollment of > 4 cohorts, should this be necessary to identify the MTD.

Sample size for the Phase 2a Expansion Cohorts will be approximately 60 patients treated at the RP2D, with accrual to be divided among up to 3 cohorts (tumor types mTNBC, N=30; SCCHN, N=15; and Sq-NSCLC, N=15; all approximations); additional patients may be entered to the Phase 2a Expansion Cohorts if fewer than 30 patients are required to establish the RP2D in Phase 1a.

The current planned initial enrollment of 15 patients per cohort (or cohort subgroup in the case of mTNBC) may be expanded based on initial observation of > 2 objective responses (13% ORR) in any of the three indications to be studied. This sample size has a 35.2% power to detect a 40% ORR compared to a potential control response of 20% at a two-sided 0.05 level of significance (TABLE 5). In addition, the power is between 45-54% to detect objective response rates between 20 to 40% in a 15 patient cohort at a two-sided 0.05 level of significance (TABLE 7).

After evaluation of the initial ORR in each cohort a decision will be made to either continue to include patients with treatment-refractory advanced/metastatic malignancies without other therapeutic options on an open-label trial(e.g., if the objective response rate is  $\geq 20\%$  and responses are durable), consider alternative trial designs for further exploration of efficacy in any of the indications, or discontinue development if fewer than two (0 or 1) responses are observed in any of the three initial fifteen patient cohorts. The durability of objective responses and disease stabilization > 8 weeks will also be considered in the decision to expand cohorts or pursue other options for further development in any of the three indications (TABLE 4). See also **Appendix I**.

TABLE 5: TEST OF NULL AT 0.05 LEVEL (TWO SIDED) USING NORMAL APPROXIMATION Power (%) for specified N (Computed using EAST 6.4)												
Null (π 0 )	Null $(\pi_0)$ True $(\pi)$ N=15 N=20 N=34 N=40											

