0.20	0.30	13.2	16.3	24.6	28.1							
	0.40	35.2	44.7	66.3	73.3							
	0.50	64.2	76.5	93.8	96.7							
	0.60	88.5	95.5	99.7	99.9							

TABLE 6: SMALLEST VALUE OF P (%) FOR STATISTICAL SIGNIFICANCE (Level 0.05, 2-Sided)													
πο	π 0 N=15 N=20 N=34 N=40												
0.20	45.2	41.7	36.2	35.0									
0.25	50.4	46.9	41.6	40.2									
0.30	55.2	51.9	46.8	45.5									
0.35	59.9	56.8	51.8	50.5									
0.40	64.3	61.4	56.7	55.5									
0.45	68.6	65.8	61.4	60.2									
0.50	72.6	70.1	66.0	64.9									

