## **APPENDIX I**

## Sample Size Considerations

The sample size considerations are presented for estimation and testing with respect to the response rate for efficacy, i.e., inference regarding the true probability of response. The normal approximation to the binomial distribution is used, unless otherwise specified.

Let  $\pi$  denote the true unknown probability of interest. The goal is to conclude that this probability exceeds a specified value ( $\pi$ 0).

Testing the null hypothesis H0:  $\pi = \pi 0$  against the one-sided alternative hypothesis H1:  $\pi > \pi 0$  can be used to achieve this goal. This test is performed at the 2.5% level, which is equivalent to testing the two-sided alternative at the 5% level.

The test procedure is to conclude that the observed result is statistically significant if:

$$n1/2 (p-\pi 0)/(p(1-p))1/2 > 1.96$$
,

where p is the observed proportion of responses from n subjects.

The smallest value of p required to have statistical significance for specified values of  $\pi 0$  and n is the solution to this inequality, but a "closed expression" is not possible. This value of p is determined by evaluating n1/2 (p- $\pi 0$ )/(p(1-p))1/2 and then comparing this value to 1.96, and is given in the following table.

SMALLEST VALUE OF P (%) FOR STATISTICAL SIGNIFICANCE (Level 0.05, 2-Sided)									
πο	π 0 N=15 N=20 N=34 N=40								
0.20	45.2	41.7	36.2	35.0					
0.25	50.4	46.9	41.6	40.2					
0.30	55.2	51.9	46.8	45.5					
0.35	59.9	56.8	51.8	50.5					
0.40	64.3	61.4	56.7	55.5					
0.45	68.6	65.8	61.4	60.2					
0.50	72.6	70.1	66.0	64.9					

Other alternatives for this examination are power considerations: (1) determination of power for specified n and assumed true value of  $\pi$ , (2) determination of n required to have power 80% or 90% for assumed true value of  $\pi$ , and (3) determination of  $\pi$  for specified n and power. The latter is related to a confidence interval (CI) because it is estimation of  $\pi$ , so the 95% CI is presented for specified values of the observed proportion of responses from n subjects (p); this is also related to the values given in the first Table. In addition to the 95% CI using the normal approximation, the 95% CI using the exact binomial method is also presented as these are presented in the protocol for p=15% and 25%.

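### The 35.2% power used to justify 15 patients per cohort belongs to a test that no section plans to run; the response counts that guide the 15-patient decision have no stated probabilities

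*Combined protocol and SAP*

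**What the plan says.** Section 14.2 plans an initial 15 patients in each cohort, or in each mTNBC subgroup, and justifies that number by power at a two-sided 0.05 level: "This sample size has a 35.2% power to detect a 40% ORR compared to a potential control response of 20" per cent. Appendix I repeats the sentence and sets out the test behind it. It states the aim as "The goal is to conclude that this probability exceeds a specified value", fixes the level ("This test is performed at the 2.5% level, which is equivalent to testing the two-sided alternative at the 5% level"), and then gives a formula introduced by "The test procedure is to conclude that the observed result is statistically significant if". Table 6, titled "SMALLEST VALUE OF P (%) FOR STATISTICAL SIGNIFICANCE", puts the threshold at 45.2% for N=15 and a null rate of 20%.

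Section 14.1, however, ends its account of Phase 2a with "No tests of statistical inference will be performed". Section 14.3.3.1 plans counts and percentages for ORR and DCR, and Kaplan-Meier estimates with 95% confidence intervals for TTP. It contains no test of ORR.

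The action at 15 patients is described in Section 14.2 by counts. A cohort may be expanded on more than 2 objective responses, which the text glosses in brackets as a 13% ORR. Continuation is illustrated by an ORR of at least 20% with durable responses. The sponsor may consider other trial designs, or "discontinue development if fewer than two (0 or 1) responses are observed". Durability and disease stabilization beyond 8 weeks also enter the decision.

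**The concern.** A sample-size justification should describe the decision that the sample will support. Here the only probability quoted for 15 patients comes from a rule with a threshold of 7 responses, while the text that guides the decision uses thresholds of 1 and 2. A reader who takes 35.2% as the design's chance of recognising a 40% ORR, and 0.05 as its protection against a 20% ORR, is misled on both counts.

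What the sponsor needs when the first 15 patients have been assessed is the chance that a cohort lands in the stop, middle or expand range for a given true ORR. Section 14.2, Tables 5 and 6 and Appendix I give power, critical proportions, sample sizes and confidence intervals, but none of these chances. Section 14.3 promises an SAP before database lock, but that may come too late: Section 3.3 halts mTNBC subgroup recruitment at 15 patients to assess activity.

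**Working it through.** **Inputs.** n = 15 (Section 14.2). Null rate 20%, alternative 40%, stated power 35.2% (Section 14.2, Table 5). Test: √n (p − π₀)/√(p(1 − p)) > 1.96 (Appendix I). Count thresholds: 0–1 for discontinuation and more than 2 for possible expansion (Section 14.2). Patients in the expansion cohorts are not replaced (Section 9.2).

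**Step 1: reproduce 35.2%.** Using the normal approximation with the variance at the alternative, power = Φ(√15 × (0.40 − 0.20)/√(0.40 × 0.60) − 1.96) = Φ(1.581 − 1.96) = Φ(−0.379) = 35.2%. This matches Table 5. Using the variance at the null would give 49.2%, so the quoted figure belongs to the Appendix I statistic.

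**Step 2: find that test's threshold in patients.** With π₀ = 0.20, 6/15 gives 1.58 (not significant) and 7/15 gives 2.07 (significant). The test therefore needs at least 7/15 = 46.7%, in line with the 45.2% in Table 6. The exact binomial probability of 7 or more is 1.8% at a true ORR of 20% and 39.0% at 40%. No action in Section 14.2 is tied to 7 responses.

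**Step 3: compute probabilities for the counts that Section 14.2 does use.** With X ~ Binomial(15, π):

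| True ORR | 0–1 responses | Exactly 2 | At least 3 |
|---|---|---|---|
| 5% | 82.9% | 13.5% | 3.6% |
| 10% | 54.9% | 26.7% | 18.4% |
| 20% | 16.7% | 23.1% | 60.2% |
| 30% | 3.5% | 9.2% | 87.3% |
| 40% | 0.5% | 2.2% | 97.3% |

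**Step 4: check the trigger wording.** 2/15 = 13.3% and 3/15 = 20%. More than 2 responses therefore means an observed ORR of at least 20%, whereas the bracketed 13% corresponds to exactly 2. Read literally, exactly 2 responses meets neither the expansion count nor the discontinuation count. If 2 were enough, the chance of reaching the expansion count would be 23.1% + 60.2% = 83.3% at a true ORR of 20%, and 2.2% + 97.3% = 99.5% at 40%.

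**The case against.** The strongest reply is that the decision is not a pure count rule. Expansion is permitted rather than required, the continuation threshold is given as an example and asks for durable responses, stabilization beyond 8 weeks is weighed, and alternative designs are a third outcome. This stands. A reader might infer from the table that the design advances 60% of drugs with a 20% ORR and 97% of drugs with a 40% ORR. The documents do not support that: the table gives the chance of reaching a count, and they offer no way to calculate the effect of durability and judgement.

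A reader might also call the 60.2% a false-go rate. Section 14.2 describes 20% only as a potential control response and does not say that a drug at 20% should be dropped; its own continuation example begins at 20%. Section 2.1.3 cites about 13% partial responses with single-agent cetuximab in SCCHN after platinum. A permissive screen of 15 patients is a legitimate early-phase choice. The 83.3% and 99.5% figures depend on reading the trigger as 2 or more, which the operative wording does not say.

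The sentence in Section 14.1 closes a paragraph on summarizing Phase 2a data with Phase 1a patients at the same dose, so its scope could be narrower than it sounds. But it is worded generally, and Section 14.3 contains no test that would give Appendix I an application.

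Finally, uncertainty at n = 15 is not hidden. Appendix I gives exact 95% intervals of 4.3–48.1% for an observed 20% and 16.3–67.7% for an observed 40%. These intervals show precision, not the chance of each course of action.

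**Conclusion.** The point holds in this form: the 35.2% is computed correctly but is not the probability of any action that the plan describes, and the counts that guide the 15-patient decision have no stated probabilities. The gap is large. The quoted test needs 7 responses and has 35.2% power at a 40% ORR; the expansion count needs 3 and is reached with probability 97.3% at 40% and 60.2% at 20%. Sections 14.1 and 14.2 with Appendix I also disagree, at least on their face, about whether a test exists.

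The figures assume independent patients with a common true ORR, all 15 contributing to the count, and the literal reading of more than 2. They describe the count component only.

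This should be fixed, but it does not undermine the trial. Phase 2a is uncontrolled, its activity objective is preliminary (Section 3.2.1), and no planned estimate changes.

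**What to change.** 1. In Section 14.2 and Appendix I, reconcile the more-than-2 trigger with the bracketed 13%, and say what follows from exactly 2 responses in 15.
2. Replace the 35.2% sentence in both places with the table above (recut if step 1 changes the threshold), labelled as the count component only, with durability, stabilization and judgement applied in addition.
3. Make Section 14.1 agree with Section 14.2 and Appendix I. Either label Tables 5 and 6 and the Appendix I test as illustrative, with no test supporting the 15-patient decision, or state where that test will be applied and limit the sentence in Section 14.1 accordingly.

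The cost is a few lines of text and one small table, with no change to sample size or conduct. The drawback for the sponsor is that the design becomes visibly permissive at a 20% ORR.

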### 14.3. Statistical Analysis

Statistical analyses will be carried out using SAS Version 9.3 or higher. The statistical methods for this study will be described in a detailed statistical analysis plan (SAP) which will be finalized prior to database lock. Any deviations from the planned analysis will be justified in the final study report.

# **FORBIUS**

Patient characteristics including race, ECOG PS, and age will be described using descriptive statistics. Frequency tables will summarize the incidence and type of treatment-related AEs by severity, experienced by patients who received at least 1 dose of study drug (Safety population).

Continuous variables, including baseline characteristics, will be summarized by reporting the number of observations, mean, standard deviation, median, minimum and maximum. Categorical/discrete variables will be summarized using frequency tables showing the number and percentage of patients within a particular category. Time-to-event data will be summarized using the Kaplan-Meier method. Withdrawals of patients from study medication and causes of death will also be reported as listings and summary tables.

Unless indicated otherwise, summary statistics will be reported for observed data only. Missing data will not be imputed. If a baseline value is missing, no change from baseline will be calculated. Baseline is defined as the last available observation prior to the first administration of study drug on Cycle 1/Week 1/Day 1.

### 14.3.1 Analysis Sets

- Safety analyses will be conducted on patients receiving any amount of a AVID100 dose (partial or complete). Patients completing Cycle 1 in the absence of a DLT, will be considered to have tolerated the AVID100 regimen. Patients must receive their planned dose of AVID100 during Cycle 1 plus 2 weeks of follow-up in order to be considered evaluable for tolerability, unless dose reduction, interruption, or discontinuation was the result of a DLT.
- PK analyses will be performed in Dose Escalation Cohorts and Expansion Cohorts on patients who receive any amount of their assigned dose of AVID100 and have an adequate number of concentration determinations to allow for PK calculation.
- All enrolled\* patients will be evaluated for antineoplastic activity. In addition, patients who complete Cycle 2 (6 weeks) of treatment, receive at least 2 planned doses during that period, and have a follow-up assessment of disease status will be considered evaluable for assessment of antineoplastic activity. Patients who are withdrawn from the study before completion of Cycle 2 because of progressive disease also will be included in assessments of antineoplastic activity.

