	returned to baseline status, or been adequately explained, and that no longer term deleterious effects have become evident.  Any patient who develops pulmonary fibrosis will be followed at approximately 3 month intervals for up to 2 years to assess the course of the disease and evaluate potential reversibility of this finding.  • In the event of an ongoing OR or SD at the EOT, response assessments based on tumor marker and imaging studies will continue to be performed every 3 months during the first year and every 6 months thereafter, until PD or another therapeutic intervention is initiated, so that data may be collected on the duration of stabilization or response, as well as on the overall TTP.
ANALYSIS PLAN	
Safety/Tolerability	Safety analyses are to be conducted on patients receiving any amount of a dose of AVID100.
Antineoplastic Activity	Patients who complete Cycle 2 (6 weeks) of treatment, receive at least 2 planned doses during that period, and have a follow-up assessment of disease status will be considered evaluable for assessment of antineoplastic activity. Patients who are withdrawn from the study before completion of Cycle 2 because of progressive disease also will be included in assessments of antineoplastic activity.
TRIAL REPORTING	
Final Study Report	Final integrated clinical/statistical study report to be prepared following study completion.

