# 6.3. **Cohort Management**

For the purposes of this study, "enrollment" is defined as patient registration to participate in this trial; at this time the patient's study identification code and dose cohort will be assigned.

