## 9.2. **Replacements**

Phase 1a: Dose-Escalation: Should a patient discontinue treatment with study drug for reasons other than the occurrence of a study drug-induced toxicity prior to completing Cycle 1 a replacement patient will be obtained using the original eligibility criteria. Patients discontinued due to study drug-associated toxicity will not be replaced.

Note: Patients must receive their full planned dose of AVID100 during Cycle 1 in order to be considered evaluable for tolerability, unless dose reduction, interruption, or discontinuation is the result of a DLT. Patients receiving < 1 full planned study drug dose plus 3 weeks of follow-up during Cycle 1 for reasons other than toxicity will be replaced.

Phase 2a Dose-Expansion: It is not planned to replace any patients in the 3 dose-expansion cohorts.

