#### Phase 2a

As a primary objective of the Phase 2 portion of the trial, OR, duration of OR and SD, as well as TTP will be assessed and calculated, wherever possible, according to standard response criteria (see **Appendix F**; Measurement of Effect). Frequency counts and percentages will be presented for an objective response rate (ORR) and disease control rate (DCR). For analysis of TTP, the median time to event and 95% confidence intervals will be calculated using the Kaplan-Meier method.

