#### **Response Calculations**

In the event of an OR (CR or PR) the duration of the OR will be determined from the day the initial response is observed (using screening/baseline images for comparison) to the day that progression is observed. Duration of SD (minimum duration of not less than 8 weeks) will also be assessed using the time from the first dose of AVID100 to the day that PD is documented.

The ORR will be calculated as the proportion of patients who achieve either a complete response or a partial response (CR+PR). ORR, time to OR, and duration of OR will be determined.

DCR will be calculated as the proportion of patients who achieve either a complete response, partial response, or disease stabilization for a minimum of 8 weeks (CR+PR+SD).

TTP will be measured from the treatment start date (date of first dose) to either the date the patient is first recorded as having disease progression (even if the patient went off treatment because of toxicities), or the date of death if the patient dies due to any cause before progression. If a patient is lost to follow-up, the patient will be censored as of the date of last contact. Patients who start a new treatment before they progress will be censored as of the date of start of the new treatment. If a patient has not progressed nor died, time to progression is censored at the date of last follow-up. TTP will be analyzed using the method of Kaplan and Meier.

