## A. DEFINITIONS

Evaluable for Toxicity: All patients will be evaluable for toxicity from the time of their first treatment with study drug.

**Evaluable for Objective Response:** Only those patients who have measurable disease present at baseline, have received at least one cycle of therapy, and have had their disease re-evaluated will be considered evaluable for response. These patients will have their response classified according to the definitions stated below.

Note: Patients who exhibit objective disease progression prior to the end of cycle 1 will also be considered evaluable.)

**Evaluable Non-Target Disease Response:** Patients who have lesions present at baseline that are evaluable but do not meet the definitions of measurable disease, have received at least one cycle of therapy, and have had their disease re-evaluated will be considered evaluable for non-target disease. The response assessment is based on the presence, absence, or unequivocal progression of the lesions.

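### No analysis set is named as primary for the Phase 2a ORR and DCR, and the rules for confirmation, evaluation interval and 8-week stable disease differ between sections

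*Combined protocol and SAP*

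**What the plan says.** Section 3.2.1 makes preliminary antineoplastic effect part of the Phase 2a primary objective. Three descriptions of who is assessed for it are in current text.

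- Section 14.3.1: all enrolled "patients will be evaluated for antineoplastic activity. In addition, patients who complete Cycle 2 (6 weeks) of treatment", with at least two planned doses and a later disease assessment, are evaluable, as are patients withdrawn early for progression. Under section 6.3, enrollment "is defined as patient registration to participate in this trial".
- Synopsis, Antineoplastic Activity: only the narrower group, described as "Patients who complete Cycle 2 (6 weeks) of treatment, receive at least 2 planned doses during that period, and have a follow-up assessment". The synopsis then adds early progressors: "Patients who are withdrawn from the study before completion of Cycle 2 because of progressive disease also will be included". All enrolled patients are not mentioned.
- Appendix F, section A: "Only those patients who have measurable disease present at baseline, have received at least one cycle of therapy, and have had their disease re-evaluated" are evaluable for response, plus patients who progress before the end of Cycle 1.

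Section 14.3.3.1 then says "Frequency counts and percentages will be presented for an objective response rate (ORR) and disease control rate (DCR") and "The ORR will be calculated as the proportion of patients who achieve either a complete response or a partial response (CR+PR"), without naming a set. Section 14.3 restricts summaries to observed data without imputation unless stated otherwise. Section 9.2 adds: "It is not planned to replace any patients in the 3 dose-expansion cohorts".

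Three measurement rules also differ:

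- **Confirmation of CR or PR.** The text of section 7.4.3 sets 4 weeks (+7 days) after first response. The visit list in the same section, Table 7 note 19 and Appendix F set a 4-week minimum with no upper limit.
- **Evaluation interval.** Appendix F says every 8 weeks. Sections 2.4.2 and 7.4.3 and Table 7 give a 6-week schedule (end of Cycle 2 and each even cycle after it).
- **Stable disease (SD).** DCR needs 8 weeks of stabilization (section 14.3.3.1). Table 7 note 19 wants the SD criteria met at 8 weeks or later. Section 14.3.3.1 and Appendix F, section E measure SD from start of treatment to progression. Section 7.4.3 can be read either way.

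**The concern.** The three sets differ in a predictable direction. The Cycle 2 set removes patients who leave early for anything other than progression: toxicity, death, or deterioration without documented progression. Almost all of these are non-responders, and they are not replaced, so using this set raises the reported ORR. Appendix F removes fewer patients. Even the all-enrolled reading is incomplete, because the observed-data rule in section 14.3 leaves open whether an unassessed patient stays in the denominator.

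The trial is open-label, and recruitment to each mTNBC subgroup halts at 15 patients so that activity can be assessed (sections 3.3 and 4.2). Section 14.2 ties further steps to the initial ORR in each cohort. The SAP promised in section 14.3 need only be final before database lock. The denominator could therefore be settled after responses are known.

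The confirmation and SD rules have a separate effect: they decide whether the same patient, with the same scans, counts as a responder or as disease control.

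**Working it through.** **Inputs.** Planned n = 15 per cohort or mTNBC subgroup (section 14.2). Cycles last 21 days. End-of-cycle scans fall in the week before Day 1 of the next cycle or on that day (section 7). The plan gives no rate of early exit without progression, so 1 to 5 of 15 is an assumption.

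**The plan's own figure.** Appendix I gives an exact 95% CI of 4.3 to 48.1 for an observed 20% at N=15. Clopper-Pearson for 3/15 gives 4.3 to 48.1, so it reproduces.

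**Denominator effect.** ORR = responders / n.

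| Responders | n=15 | 14 | 13 | 12 | 11 | 10 |
|---|---|---|---|---|---|---|
| 3 | 20.0% | 21.4% | 23.1% | 25.0% | 27.3% | 30.0% |
| 2 | 13.3% | 14.3% | 15.4% | 16.7% | 18.2% | 20.0% |

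**All three sets on one cohort (assumed).** Of 15 registered patients, one is never dosed, one stops in Cycle 1 for toxicity without a scan, and one stops for toxicity after Cycle 1 with a scan that does not show progression. All enrolled: 15. Appendix F drops the first two: 15 − 2 = 13. The Cycle 2 set also drops the third: 12. Three responders are then 3/15 = 20.0%, 3/13 = 23.1% or 3/12 = 25.0%.

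**Confirmation.** 4 weeks = 28 days, and +7 gives 35. Without delays, Cycle 3 Day 1 is study day 43 and Cycle 5 Day 1 is study day 85. The two routine scans therefore fall on days 36–43 and 78–85. The gap is nominally 85 − 43 = 42 days, with a range of 78 − 43 = 35 to 85 − 36 = 49. A response first seen at the end of Cycle 2 and confirmed at the next routine scan always meets the 4-week minimum, but meets the 28–35 day window only at the shortest gap. A dedicated confirmatory scan at days 28–35 meets both rules. If a third response is confirmed at day 42, the count is 3 under the minimum-only rule and 2 under the window. Section 14.2 allows expansion on more than 2 responses.

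**Stable disease.** 8 weeks = 56 days. For a patient on treatment without delays, the first scan is 35–42 days after first dose and the second 77–84 days. Take SD at week 6 and progression at week 12. Under note 19, no scan at 56 days or later shows SD, so the patient does not count. Under section 14.3.3.1 and Appendix F, section E, first dose to progression is about 84 days, so the patient counts. Each such patient moves DCR by 1/15 = 6.7 points. An 8-week schedule, as in Appendix F, would put the first scan at about day 56, so the interval conflict feeds into this one.

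**The case against.** The best reply is that section 14.3.1 already answers the question. It sits under the heading for analysis sets, assigns all enrolled patients to activity and adds an evaluable set. On that reading the synopsis is an abbreviation, and Appendix F is a summary of general RECIST guidance that section 14.3.3.1 cites for response criteria, not for a population. A SAP is promised, no inferential tests are planned (section 14.1), and expansion is discretionary. Much of this stands. A reader might infer that no set at all is assigned to activity, and section 14.3.1 does not support that. What is missing is which of its two groups is primary, how unassessed patients count, and agreement with the synopsis.

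Three other inferences also go too far.

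- That the 4 weeks (+7 days) window is nearly unattainable. Sections 7.4.3 and 7.4.4 list a separate assessment at least 4 weeks after a response, so a site can scan inside the window. The conflict bites only when that scan is late or the routine scan is used instead, and the plan gives no frequency for either.
- That the 13% in section 14.2 (2/15) shows the intended denominator. It is attached to more than 2 responses, and 3/15 is already 20.0%, so it does not match its own rule and proves little.
- That the choice of set changes the go/no-go decision. The rules on more than 2 responses, and on 0 or 1, are counts. The 20% criterion is only an example, joined to durability.

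**Conclusion.** The point holds as a conflict of definitions that should be fixed. It is not a challenge to the sample size or power. The primary set for ORR and DCR is unnamed, the synopsis contradicts section 14.3.1, and Appendix F matches neither. With 1 to 5 of 15 patients assumed non-evaluable, three responders read as 21.4% to 30.0% instead of 20.0%; two responders reach 20.0% only if five are dropped. These shifts lie inside the exact interval of 4.3 to 48.1, so what is at stake is which number was specified in advance.

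The confirmation conflict can change the response count itself, but only for responses confirmed after day 35. The SD conflict is worth 6.7 DCR points per affected patient at n=15. The Appendix F interval is an isolated mismatch with an otherwise consistent 6-week schedule. The timing results assume 21-day cycles without delay.

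**What to change.** Make these changes before the 15-patient activity reviews.

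- In sections 14.3.1 and 14.3.3.1, name all enrolled patients in each cohort or mTNBC subgroup as the primary set for ORR and DCR. Count patients without an assessment as non-responders, and state this as an exception to the observed-data rule in section 14.3. Keep the Cycle 2 set as a sensitivity analysis.
- Align the synopsis and Appendix F, section A with this.
- Define confirmation in one way throughout: any scan at least 4 weeks after first response.
- State one 8-week SD rule for DCR: either a scan still showing SD at 8 weeks or later, or time from first dose to progression. Align section 7.4.3, Table 7 note 19, section 14.3.3.1 and Appendix F.
- Reconcile the Appendix F evaluation interval with sections 2.4.2 and 7.4.3 and Table 7.

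The cost is wording only, with no added patients, visits or scans. The reported ORR and DCR may be slightly lower and, because enrollment means registration, a registered but undosed patient counts as a non-responder. A treated-patient set would also remove the ambiguity. All enrolled is preferred because section 14.3.1 already lists it first.
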